6.2.1.1 Dosage, Administration, and Schedule

Talimogene laherparepvec must be prepared and administered by a qualified healthcare professional. Subjects should be assessed clinically for adverse events/toxicity prior to each dose using the Common Terminology Criteria for Adverse Events (CTCAE) version 3.0 ([Appendix A](#)). Complete blood count with differential and chemistry panels including liver function laboratory tests (**such as** ALT, AST, and total bilirubin) should be obtained according to the Schedule of Assessments (see [Table 2](#)) and the results should be checked before scheduled **doses as per the requirements described in the Schedule of Assessments**. Dosing will occur only if these test values are acceptable, per [Section 6.2.1.2](#).

Talimogene laherparepvec will be administered by intralesional injection only into injectable cutaneous, subcutaneous, and nodal tumors, with or without image ultrasound guidance. Talimogene laherparepvec must not be administered into visceral organ metastases. The initial dose of talimogene laherparepvec is up to 4.0 mL of 10^6 PFU/mL. Subsequent doses of talimogene laherparepvec are up to 4.0 mL of 10^8 PFU/mL.

The first cycle of talimogene laherparepvec will be 21 (+ 5) days. Subsequent cycles of talimogene laherparepvec will be 14 (\pm 3) days. On day 1 of cycle 1 the first dose of talimogene laherparepvec will be up to 4.0 mL of 10^6 PFU/mL. The second injection up to 4.0 mL of 10^8 PFU/mL, should be administered 21 (+ 5) days after the initial injection (ie, no sooner than day 22 but should not be delayed more than 5 days after the 21-day time point). Subsequent injections up to 4.0 mL of 10^8 PFU/mL should be given every 14 (\pm 3) days.

The maximum volume of talimogene laherparepvec administered at any dose is 4.0 mL for any individual lesion. The maximum dose in any treatment is 4.0 mL. Investigators are encouraged to use the maximum amount whenever lesions allow. Dose reduction for adverse events is not allowed. However, if in the course of administration of talimogene laherparepvec the subject cannot tolerate the full dose due to an

injection-related adverse event such as pain, the total volume given should be recorded, and the reason for intolerance should be documented as an adverse event.

The recommended volume of talimogene laherparepvec to be injected into the tumor(s) is dependent on the size of the tumor(s) and should be determined according to the injection volume guideline in [Table 1](#). The tumor size assessment should be done by clinical exam using ruler or caliper for cutaneous and palpable and protruding subcutaneous and nodal lesions, or by measurements under ultrasound of deep-seated subcutaneous and nodal lesions.

Table 1. Talimogene Laherparepvec Injection Volume Guideline Based on Tumor Size

Tumor Size (longest dimension)	Maximum Injection Volume
> 5.0 cm	4.0 mL
> 2.5 cm to 5.0 cm	2.0 mL
> 1.5 cm to 2.5 cm	1.0 mL
> 0.5 cm to 1.5 cm	0.5 mL
≤ 0.5 cm	0.1 mL

At baseline, if there are ≥ 2 lesions, one **cutaneous, subcutaneous or nodal** lesion (ie, the lesion considered lowest priority for injection) should be left uninjected at least until it is biopsied at week 6 (see [Section 7.2.2](#)). **(No biopsy will be taken at week 6 for subjects with 1 lesion present at baseline)**. All other reasonably injectable lesions (cutaneous, subcutaneous, and nodal disease that can be injected with or without ultrasound guidance) should be injected with the maximum dosing volume available on an individual dosing occasion ([Table 1](#)). On each treatment day, prioritization of injections is recommended as follows (aside from leaving one lesion uninjected until it is biopsied at week 6):

- any new injectable tumor that has appeared since the last injection
- by tumor size, beginning with the largest tumor
- any previously uninjectable tumor(s) that is now injectable, including the previously uninjected lesion(s) after the biopsy at week 6 if now injectable

It is recommended that each lesion should receive the maximum amount possible to inject due to tumor properties at each visit before moving on to the next lesion, using the prioritization model above and the injection volume guideline based on tumor size per [Table 1](#). Lesions should be injected until the maximum volume per day (4.0 mL) has been reached or there are no further injectable lesions, whichever comes first.

A subject will be treated with talimogene laherparepvec until the subject has achieved a CR, all injectable tumors have disappeared, clinically significant (resulting in clinical deterioration or requiring change of therapy) disease progression beyond 6 months of treatment, per modified World Health Organization (WHO) response criteria (Appendix D), or intolerance of study treatment, whichever occurs first. Due to the mechanism of action, subjects may experience growth in existing tumors or the appearance of new tumors prior to maximal clinical benefit of talimogene laherparepvec. Therefore, dosing should be continued for at least 6 months from the time of initial dose, provided that the subject has no evidence of clinically significant deterioration of health status requiring discontinuation of treatment with talimogene laherparepvec and is able to tolerate the treatment.

The dose, start date, and lot number of talimogene laherparepvec are to be recorded on the electronic case report form (eCRF).

6.2.1.2 Dosage Adjustments, Delays, Rules for Withholding or Restarting, Permanent Discontinuation

Dose reductions of talimogene laherparepvec are not permitted, other than with respect to a reduction in the volume injected due to a disease response.

If a subject experiences any of the following treatment-related toxicities, talimogene laherparepvec administration should be delayed until the toxicity has resolved to at least CTCAE grade 1 or has returned to baseline:

- grade 2 or greater immune-mediated adverse events, with the exception of vitiligo
- grade 2 or greater allergic reactions
- any other grade 3 or greater hematologic or non-hematologic toxicity

Subjects who are receiving talimogene laherparepvec may not receive systemic antiherpetic drugs (eg, acyclovir, valacyclovir, famciclovir), but **may receive a topically administered antiherpetic drug more than 20 cm from a talimogene laherparepvec injection site. If a subject requires treatment with systemic antiherpetic drugs (eg, acyclovir, valacyclovir, famciclovir) talimogene laherparepvec should be withheld and the investigator or designee should notify the Amgen medical monitor as soon as possible. Subject may be allowed to continue treatment after discussion between the Amgen medical monitor and the investigator to determine the appropriateness of treatment resumption.**

Dosing should be permanently discontinued if, in the opinion of the investigator, the subject develops clinical evidence of any systemic herpes infection (such as encephalitis or disseminated infection).

If the subject requires corticosteroid dosing of > 10 mg prednisone daily (or equivalent) for related toxicities, talimogene laherparepvec dosing must be withheld until the corticosteroid dose has decreased to \leq 10 mg prednisone daily (or equivalent).

All necessary supportive care shall be available to subjects except for those listed in [Section 6.8](#). Talimogene laherparepvec treatment should be continued based on the potential benefit/risk assessment of the subject.

If talimogene laherparepvec treatment is delayed by >1 week, that dose will be deemed to have been missed and the subject will proceed to the next scheduled treatment visit.

If talimogene laherparepvec dosing is delayed by more than 4 weeks from the date of the planned dose (ie, approximately 6 weeks from the previous dose) due to the occurrence of an adverse event that is considered related to talimogene laherparepvec, the subject must be permanently withdrawn from talimogene laherparepvec treatment.

If talimogene laherparepvec dosing is delayed by more than 4 weeks from the date of the planned dose (ie, approximately 6 weeks from the previous dose) for reasons other than treatment-related toxicity, the case must be reviewed by the Amgen medical monitor in conjunction with the investigator to determine if the subject can resume talimogene laherparepvec therapy.

Talimogene laherparepvec is to be permanently discontinued for subjects meeting any of the following criteria:

- The subject, for any reason, requires treatment with another anticancer therapeutic agent for treatment of the study disease (other than the exceptions noted in [Section 6.5](#)). In this case, discontinuation from the treatment occurs immediately upon introduction of the new agent.
- Clinically relevant disease progression beyond 6 months of treatment occurs as defined per the modified WHO response criteria ([Appendix D](#)).
- A grade 2 or greater immune-mediated adverse event (with the exception of vitiligo) or allergic reactions attributed to talimogene laherparepvec that would require a dose delay of greater than 4 weeks from the date of the planned dose (ie, approximately 6 weeks from the previous dose).

Note: immune-mediated glomerulonephritis, vasculitis, and pneumonitis and exacerbation of psoriasis have been observed in subjects receiving talimogene laherparepvec in clinical trials. Most of these subjects had a history of other autoimmune disease and/or prior treatment with agents that offered plausible

alternative etiologies, however, immune-mediated adverse events can potentially involve any organ system.

- Any other talimogene laherparepvec-related non-hematologic or hematologic toxicities grade 3 or greater occur that, in the opinion of the investigator, would require a dose delay of greater than 4 weeks from the date of the planned dose (ie, approximately 6 weeks from the previous dose).
- The subject develops clinical evidence of any systemic herpes infection (such as encephalitis or disseminated infection).
- A female subject becomes pregnant or fails to use acceptable method(s) of effective contraception (for those subjects who are able to conceive) **including but not limited to male or female latex condom to avoid potential viral transmission during sexual contact.**
- A female subject breast feeds while on study treatment.
- Concurrent medical illness that, in the judgment of the investigator, would make continued treatment with talimogene laherparepvec dangerous for the subject.

For additional information related special warnings and precautions for the use of talimogene laherparepvec please refer to the latest version of the Talimogene Laherparepvec Investigator's Brochure.

6.3 Other Protocol-required Therapies

All other protocol-required therapies including topical anesthetic or an injectable local anesthetic medications used for pretreatment of the talimogene laherparepvec injection site that are commercially available are not provided or reimbursed by Amgen (except if required by local regulation). The investigator will be responsible for obtaining supplies of these protocol-required therapies.

Additional details regarding these protocol-required therapies are provided in the IPIM.

6.4 Concomitant Therapy

Throughout the study, investigators may prescribe any concomitant medications or treatments deemed necessary to provide adequate supportive care except for those listed in [Section 6.8](#).

All prescription and nonprescription concomitant medication administered up to 28 days prior to enrollment, on an ongoing basis **after** enrollment, as well as changes in such concomitant medication, and any new concomitant medication taken while the subject is on study, should be recorded on the appropriate case report form (CRF) until 30 days (+ 7 days) after the last dose of talimogene laherparepvec. The therapy name, indication, dose, unit, frequency, start date, and stop date will be collected.

Investigators should use supportive care agents in compliance with their respective regional label. Investigators may not use supportive care agents as part of a separate clinical trial.

6.5 Other Treatment Procedures

Treatment with talimogene laherparepvec may result in the reduction of tumor burden such that surgical resection of previously unresected lesion becomes possible. Investigators may choose to resect lesions which become suitable for resection to render the subject free of macroscopic disease. Additionally, biopsies will be taken of cutaneous, subcutaneous or **nodal** lesions for tumor analysis during study. In the event of a complete response, residual **visible** cutaneous or subcutaneous index lesions must be documented by representative biopsy to not contain viable tumor. If a subject undergoes resection of the lesion in the event other than CR, the investigator or designee should notify the sponsor medical monitor as soon as possible and the procedure should be recorded in the source document and eCRF. In these instances, if the response of other lesions is at least PR (if other lesions remain), the response should be designated PR with the date of surgery as the date of response. If no residual disease remains following surgery, this should also be noted in the eCRF, the response definition again being PR **with the date of surgery as the date of response. If no viable melanoma was found in the surgical specimen and all other tumor lesions resolved completely (if were present), the response definition will be CR with the date of surgery as the date of response.**

Local palliative radiation treatment for relief of various symptoms including, but not limited to, bleeding or pain associated with the underlying disease will be permitted at any time during the study. Subjects with local symptoms suggestive of disease progression should be evaluated for tumor response per modified WHO response criteria (see [Appendix D](#)) prior to the administration of palliative radiotherapy. If a subject undergoes local radiation, the investigator or designee should notify the sponsor medical monitor as soon as possible and the treatment should be recorded in the source document and eCRF.

If a subject demonstrates evidence of recurrent or new central nervous system (CNS) metastases, talimogene laherparepvec should be withheld and the investigator or designee should notify the Amgen medical monitor as soon as possible. Subjects may be allowed to remain on protocol after discussion between the Amgen medical monitor and the investigator to determine the appropriateness of treatment resumption provided

CNS lesions can be treated with stereotactic radiotherapy (including GammaKnife) or **resection** and if there is no change in the baseline ECOG performance status. Subjects may be allowed to reinitiate talimogene laherparepvec following treatment of CNS metastases while receiving dexamethasone or a similar corticosteroid at no more than 1.5 mg dexamethasone (or 10 mg prednisone **or equivalent**) per day. If higher doses of a steroid are used, talimogene laherparepvec must be held until that dose level is reached during the period of steroid tapering.

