6.8 Excluded Treatments and/or Procedures During Study Period

Subjects must not use any of the following therapies during screening or treatment period:

- other investigational agents or procedures
- concurrent experimental or approved anti-tumor therapies other than study drug and radiation therapy required for palliation (as noted in [Section 6.5](#))
- chronic oral or systemic steroid medication use at a dose of >10 mg/day of prednisone or equivalent (with the exception of treatment for adverse events [see [Section 6.2.1.2](#)] and CNS metastases [see [Section 6.5](#)]). Steroids with low systemic absorption [eg, triamcinolone hexacetonide] injected into a joint space is allowed)
- antiherpetic drugs (eg, acyclovir), other than if topically administered > 20 cm from a talimogene laherparepvec injection site. **If a subject requires treatment with a systemic antiherpetic drugs (eg, acyclovir, valacyclovir, famciclovir) talimogene laherparepvec should be withheld and the investigator or designee should notify the Amgen medical monitor as soon as possible. Subject may be allowed to continue treatment after discussion between the Amgen medical monitor and the investigator to determine the appropriateness of treatment resumption.**

- Subjects must not schedule any elective surgeries during the treatment period and for at least 30 days after the last administration of study drug. If a subject undergoes any unexpected surgery during the course of the study, study treatment must be withheld and the investigator or designee should notify the sponsor medical monitor as soon as possible. A subject may be allowed to resume study drug if both the investigator and sponsor medical monitor agree to restart study therapy.

The exclusion criteria describe other medications and procedures which are prohibited in this study (refer to [Sections 4.1.2](#)).

There are no prohibited therapies and procedures during the post treatment long-term follow-up period.

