Nonmeasurable Lesions:

All other lesions, including small lesions (longest diameter < 10 mm by CT/MRI/ultrasound for nodal/soft tissue disease [including lymph nodes] or < 10 mm caliper measurement by clinical exam for superficial cutaneous melanoma lesion) and

other truly nonmeasurable lesions are considered nonmeasurable and characterized as nonindex lesions. This will include any measurable lesions beyond the maximum number of 10 lesions that were not chosen as index lesions.

Lesions with Prior Local Treatment:

Tumor lesions situated in a previously irradiate area, or an area subject to other loco-regional therapy, are usually not considered measurable unless there has been demonstrated progression in the lesion.

Coalescing or splitting lesions:

- **Coalescing lesions:** When two or more index or new measurable lesions merge without distinct borders between tumors, the smaller lesion should have 0 x 0 mm recorded for the current and all future assessments with a comment indicating that the lesion coalesced with the specified lesion, and the larger lesion should have the size of the merged lesion recorded for the current assessment with a comment indicating that the lesion coalesced with the specified lesion and be followed for future assessments. When two or more nonindex or new non-measurable lesions merge, the smaller lesion should be recorded as absent for the current and all future assessments, and the larger lesion should be recorded as present for the current assessment (with a comment indicating that the lesion coalesced with the specified lesion) and followed for future assessments. If an index or new measurable lesion and a non-index or new non-measurable lesion merge, the non-index or new non-measurable lesion should be absent for the current and all future assessments while the index lesion or new measurable lesion should include both merged lesions for recording measurements with a comment indicating that the lesion coalesced with the specified lesion.

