All other lesions (or sites of disease), including any measurable lesions that were not chosen as index lesions will be identified as nonindex lesions. Nonindex lesions should be recorded and assessed qualitatively over the course of therapy.

Follow-up "Index Lesions":

At each subsequent tumor assessment, the SPD of the index lesions are added together to provide the total tumor burden.

Follow-up "Nonindex Lesions":

Nonindex disease measurements are not required and these lesions should be followed as "present," "absent," or in rare cases "unequivocal progression".

Response Criteria

Evaluation of Objective Response:

The subject response will be assessed based on the response of the index lesions and nonindex lesion, and presence or absence of new lesions. Confirmation of complete or partial response is not required. The overall response is derived from time point response assessments as described in [Table 5](#), [Table 6](#), and [Table 7](#).

Table 5. Definition of Index Lesion Tumor Response Including New Lesions

Complete Response (CR):	Complete disappearance of all index lesions, including any new tumors which might have appeared. Any residual cutaneous or subcutaneous index lesions must be documented by representative biopsy to not contain viable tumor.
Partial Response (PR):	Achieving a 50% or greater reduction in the SPD of the perpendicular diameters of all index lesions at the time of assessment as compared to the sum of the products of the perpendicular diameters of all index lesions at baseline. If any new lesions have appeared, the sum of products of the perpendicular diameters of new measurable lesions must have reduced by 50% or more from when first documented.

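### Palliative radiotherapy is allowed alongside study drug, but Appendix D has no clear rule for a lesion irradiated on study, so radiation shrinkage alone can be scored as a partial response

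*Protocol*

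**What the plan says.** **Radiotherapy is permitted.** Protocol Section 6.5: "Local palliative radiation treatment for relief of various symptoms including, but not limited to, bleeding or pain associated with the underlying disease will be permitted". No limit on timing is set. Section 6.8 bans "concurrent experimental or approved anti-tumor therapies other than study drug and radiation therapy required for palliation", so palliative radiotherapy is a named exception. Section 6.2.1.2 stops study drug when a subject "requires treatment with another anticancer therapeutic agent for treatment of the study disease (other than the exceptions noted in"; the cross-reference there is to 6.5, which appears to exempt radiotherapy here too.

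**What Section 6.5 requires around it.** A response evaluation before radiotherapy if local symptoms suggest progression, notification of the medical monitor, and recording in source and eCRF. It does not say how the lesion is scored afterwards.

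**Resection does have a scoring rule.** The preceding paragraph of Section 6.5 says: "if the response of other lesions is at least PR (if other lesions remain), the response should be designated PR", dated to the surgery, and adds rules for the case of no residual disease.

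**Appendix D.** Index lesions are up to 10 measurable cutaneous, nodal or soft-tissue lesions. PR in Table 5 means "Achieving a 50% or greater reduction in the SPD of the perpendicular diameters of all index lesions at the time of assessment" against baseline. Where new lesions exist, Table 5 adds a second condition: "the sum of products of the perpendicular diameters of new measurable lesions must have reduced by 50% or more from when first documented". Also: "Confirmation of complete or partial response is not required". The only text on irradiation, headed as concerning prior local treatment, is: "Tumor lesions situated in a previously irradiate area, or an area subject to other loco-regional therapy, are usually not considered measurable". It makes an exception where progression in the lesion has been shown.

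**The concern.** Radiation shrinks tumors. If an irradiated index lesion stays in the SPD, its shrinkage counts as response to talimogene laherparepvec. The resection paragraph shows that the authors saw the same problem for a local intervention and dealt with it, but the radiotherapy paragraph does not.

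Objective response is the response variable in the primary endpoint. A miscalled PR also feeds durable response, duration of response and the maximum decrease in index lesions. Without a rule, one site may score an irradiated subject as PR and another as unevaluable. The medical monitor is told of the radiotherapy but has no written criterion to apply.

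**Working it through.** **1. Does Appendix D exclude the lesion?** Three places could do so.

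- *Prior local treatment.* The heading points to treatment before the study, the sentence is qualified by the word usually, and measurability is categorised at baseline. It does not say that an index lesion chosen at baseline loses that status if irradiated later.
- *Unable to Evaluate (Table 5).* This covers an index lesion that was not assessed or could not be evaluated. An irradiated lesion that calipers or CT can still measure is not clearly either.
- *Table 7.* Index PR with nonindex CR, SD or NA gives overall PR. Nothing in the matrix refers to radiotherapy.

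So the literal PR rule keeps the lesion in the sum.

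**2. When does radiation alone give PR?** Let s be the irradiated lesion's share of baseline SPD and f its fractional loss of area. Suppose the other index lesions are unchanged, no new lesion fails the new-lesion condition, and nonindex status is CR, SD or NA. The fall in SPD is s × f, so PR needs s × f ≥ 0.5, that is f ≥ 0.5/s. If both diameters shrink equally, each must fall by 1 − √(1 − 0.5/s).

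| Share s | Area loss needed | Fall in each diameter |
|---|---|---|
| 1.0 (sole index lesion) | 50% | 29% |
| 0.9 | 55.6% | 33% |
| 0.8 | 62.5% | 39% |
| 0.6 | 83% | 59% |
| 0.5 | 100% | lesion must vanish |
| below 0.5 | not possible | – |

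Subjects with one lesion are foreseen: inclusion criterion 107 can be met by a single measurable lesion, and Section 6.2.1.1 omits the week 6 biopsy for subjects with one lesion at baseline.

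**3. Worked example (lesion sizes assumed).** Index lesions of 40×30 and 15×10 mm give SPD 1200 + 150 = 1350. The first is irradiated and falls to 24×18; the second grows to 18×12. SPD is now 432 + 216 = 648, or 48% of baseline: a 52% fall, scored PR although the only unirradiated lesion grew. With the irradiated lesion carried at its pre-radiotherapy size (here its baseline size), SPD is 1200 + 216 = 1416, or +4.9%: scored SD.

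**4. Two lesser routes.** Shrinkage of an irradiated *new* measurable lesion can satisfy only the second of Table 5's two PR conditions. For an irradiated *nonindex* lesion, Table 7 gives PDn for index PR with nonindex PDn, but PR for index PR with nonindex SD. Radiotherapy that averts or reverses nonindex progression can therefore move the overall call.

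**5. Size.** The protocol gives no radiotherapy frequency, so these figures are illustrative.

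- *ORR.* One subject is 1/110 = 0.9 points. From 29/110 (26.4%, exact 95% CI 18.4–35.6), one false PR gives 30/110 (27.3%, 19.2–36.6) and three give 32/110 (29.1%, 20.8–38.5).
- *Power.* The Section 10.2 example is a one-sided Fisher exact test at 5%, taken as 50 per CD8 group, with 13.2% against 39.6%. Full enumeration gives 88.4%, reproducing the stated 88%. One extra responder in each group (15.2% against 41.6%) gives 87.0%. If a proportion q of non-responders in both groups is miscalled, p becomes p + q(1 − p), and power is 86.0% at q = 2% and 82.4% at q = 5%. The last case means about 3.7 false PRs per 100 subjects, a rate for which the documents give no basis.

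**The case against.** The best reply is that Appendix D, read sensibly, already covers this. The text on coalescing and splitting lesions, directly after the irradiation sentence, governs follow-up, so that part of the appendix is not confined to baseline. A lesion in an irradiated field that is no longer measurable could be called unable to evaluate, and Table 7 would then give UE rather than PR unless there is nonindex progression. That is a reasonable reading, but a site has to infer it.

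Exposure is also limited, and this stands. Only cutaneous, nodal or soft-tissue lesions enter the SPD, bone metastases are excluded at entry, and CNS disease has its own paragraph. Radiotherapy to visceral, bone or CNS disease cannot lower the SPD. Section 6.2.1.1 gives larger lesions priority for injection, so shrinkage in a large irradiated lesion would often be mixed drug and radiation effect.

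Redaction is a further limit. The readable SAP gives no derivation of ORR, and blacked-out text in Sections 6, 10.3, 11.1 and 11.4 may contain a radiotherapy rule. Even so, sites score from Appendix D.

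A reader might infer that radiotherapy ends tumor assessment and so loses later responses, because Table 2 footnote x counts local therapies as anti-cancer therapy. The documents do not support this well. Footnote x is attached to a row that records therapy at the safety and survival follow-up visits. The stopping rule is in footnotes q and r, and Section 6.8 treats palliative radiotherapy as a permitted exception.

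**Conclusion.** The point holds as a gap in the definition of response: the stated PR rule, followed literally, can credit radiation shrinkage to study drug in the response variable of the primary endpoint. It needs an irradiated cutaneous, nodal or soft-tissue index lesion holding at least half of baseline SPD, with the conditions in step 2 met.

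The effect is probably small. It is 0.9 ORR points per subject, against an exact interval about 17 points wide, and how many subjects would be affected is unknown.

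Two stronger conclusions are not supported. The 88% power is not wrong: it reproduces, and it belongs to one example test in a descriptive study. Nor do the documents suggest miscoding concentrated in one CD8 group. CD8 density is read centrally, blinded to outcome (Section 7.3.2), and biomarker results are kept out of the medical record (Section 7.5), so CD8 cannot direct radiotherapy. A one-sided effect would need an indirect prognostic link. Misscoring spread over both groups mainly adds noise.

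This is worth correcting as a cheap improvement. It does not undermine the design.

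**What to change.** 1. In Appendix D, and in the response derivation if it is not already there: from the date of on-study radiotherapy, an irradiated index or new measurable lesion gets no shrinkage credit toward PR, CR or maximum decrease. It is carried at its last pre-radiotherapy size, and growth above that size still counts.
2. An irradiated nonindex lesion gets no credit toward CR. Progression recorded before radiotherapy is not reversed by that lesion's later shrinkage. Progression that radiotherapy averts before it is recorded cannot be recovered by a scoring rule; item 4 addresses that case.
3. Record the irradiated lesion and the date. Section 6.5 requires the treatment to be recorded but does not mention the lesion.
4. Add a sensitivity analysis of ORR and of the CD8 correlation that counts only responses documented before any radiotherapy.
5. As a minor clarification, state in Table 2 footnotes q and r that palliative radiotherapy under Section 6.5 is not a new anticancer therapy that ends assessment.

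The cost is one paragraph, one clause in two footnotes, possibly one eCRF field, and one sensitivity table. Access to radiotherapy and the resection rule are unchanged. The downside is that ORR may be slightly lower and genuine drug shrinkage in an irradiated lesion is not credited. In particular, a subject whose sole index lesion is irradiated before response could no longer become a responder. Scoring such lesions as UE is an alternative convention; either is acceptable if stated in advance.
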